#### *8.4.8 Adverse Event Reporting*

Grading and attribution of AEs captured in the database will be determined by the Principal Investigator or Associate Investigator's designated on the delegation log.

#### *8.4.9 Serious Adverse Event Reporting*

The study investigator will report to the sponsor any SAE occurring after the start of intervention, whether or not considered study intervention related, including those listed in the protocol or investigator brochure and must include an assessment of whether there is a reasonable possibility that the study intervention caused the event.

All SAEs will be followed until satisfactory resolution or until the site investigator deems the event to be chronic or that the participant is stable.

The study sponsor will be responsible for notifying the Food and Drug Administration (FDA) of any unexpected fatal or life-threatening suspected adverse reaction as soon as possible, but in no case later than 7 calendar days after the sponsor's initial receipt of the information. In addition, the sponsor must notify FDA and all participating investigators in an Investigational New Drug (IND) safety report of potential serious risks, from clinical trials or any other source, as soon as possible, but in no case later than 15 calendar days after the sponsor determines that the information qualifies for reporting using a MedWatch Report (FDA Form 3500).

### **Reports to the IRB and CD**

#### Expedited Reporting

Events requiring expedited reporting will be submitted to the IRB per Policy 801 "Reporting Research Events".

*Abbreviated Title: IQ in sickle cell disease*

*Version Date: May 5, 2023*

**Reports to the IRB at the time of Continuing Review:**

The PI or designee will refer to HRPP Policy 801 “Reporting Research Events” to determine IRB reporting requirements.

**Reports to the CD:**

The PI or designee will refer to NHLBI DIR Policy to determine CD reporting requirements and timelines.

**Reports to the DSMB**

The NHLBI DSMB as the independent data safety monitoring committee will review and approve the protocol before the enrollment. SAEs that meet the definition of an Unanticipated Problem will be submitted to the DSMB within 7 days of the investigator being notified of the event. DSMB will have access to safety data upon request any time. The monitoring plan will be developed and approved by the DSMB before enrollment.

***8.4.10 Events of Special Interest***

N/A

***8.4.11 Reporting of Pregnancy***

In the event a subject becomes pregnant while on study, this event will be reported to the IRB and Clinical Director as a protocol deviation. Monitoring of the pregnancy thru chart review (per HIPPA guidelines) will continue until conclusion of the pregnancy, and then subject will be taken off study.

**8.5 UNANTICIPATED PROBLEMS**

***8.5.1 Definition of Unanticipated Problems (UP)***

Any incident, experience, or outcome that meets all of the following criteria:

- Unexpected in terms of nature, severity, or frequency given (a) the research procedures that are described in the protocol-related documents, such as the Institutional Review Board (IRB)-approved research protocol and informed consent document; and (b) the characteristics of the participant population being studied; and
- Related or possibly related to participation in the research (“possibly related” means there is a reasonable possibility that the incident, experience, or outcome may have been caused by the procedures involved in the research); and
- Suggests that the research places participants or others (which many include research staff, family members or other individuals not directly participating in the research) at a greater risk of harm (including physical, psychological, economic, or social harm) than was previously known or expected.

*Abbreviated Title: IQ in sickle cell disease*

*Version Date: May 5, 2023*

### *8.5.2 Unanticipated Problem Reporting*

The investigator will report unanticipated problems (UPs) to the NIH Institutional Review Board (IRB) as per Policy 801.

### *8.5.3 NIH Intramural IRB Reporting of IND Safety Reports*

Only IND Safety Reports that meet the definition of an unanticipated problem will need to be reported to the NIH Intramural IRB.

## **9 STATISTICAL CONSIDERATIONS**

### **9.1 STATISTICAL HYPOTHESIS**

Treatment with IQ will blunt systemic inflammation and coagulation activation in sickle cell disease patients.

**Primary Endpoint(s):** The primary outcome will be the change in the plasma soluble P-selectin comparing the baseline to IQ response after 28 days in patients with SCD.

### **9.2 SAMPLE SIZE DETERMINATION**

This is a study designed to assess the effect of IQ on plasma soluble P-selectin in subjects with stable SCD at baseline. The mean baseline soluble P-selectin measurement in a cross-sectional study of SCD patients ( $n = 29$ ) in steady state was 30 ng/ml with standard deviation of 8.4 (see preliminary data Figure 4). Follow-up measurements from the same individuals had mean values of 29 ng/ml and standard deviation of 8.4 with intra-person correlation of 0.60 for the two measurements. The proposed analysis is an analysis of covariance model with follow-up P-selectin measurement (i.e. post-treatment measurement) as the dependent variable with baseline measurement and treatment assignment as the covariates. A 25% reduction in P-selectin (i.e. an 7.25 ng/ml decline from an average value of 29 ng/ml) is the hypothesized treatment effect for IQ proposed to achieve a clinically meaningful reduction in thrombosis risk. Under these conditions a total of 40 respondents (20 per arm) is needed to obtain power of 90%. Based on these considerations we request an accrual ceiling to the study intervention portion of the study of 46 individuals to compensate for loss to follow-up or inaccurate sample size assumptions.

In the table below, we present power calculations for various scenarios. With 20 subjects on IQ and 20 on placebo, the study will have >90% power to detect a difference of 7.25 ng/ml in the mean baseline to 4-week changes between the two study groups. Furthermore, even with only 34 subjects (17 in each arm), the study will have >85% power to detect a mean change of 7.25 ng/ml. Therefore, we request approval to enroll up to a total of 46 subjects to: 1) account for potential diluting effects of possible treatment non-compliance, and/or study dropouts, 2) provide a buffer against possibly inaccurate sample size assumptions, and 3) provide power to test our hypothesis in the subgroup of per-protocol patients who avoid crises that may distort their P-selectin and other measurements (see section 9.3).

Table 4

Analysis Method	Anticipated P-selectin reduction	Power	Required Sample Size per arm
ANCOVA	25%	80%	15
ANCOVA	25%	85%	17
ANCOVA	25%	90%	20

### 9.3 POPULATIONS FOR ANALYSES

The primary analysis will be conducted among patients with SCD that are randomized. The occurrence of the following clinical events that are related to the underlying disease biology may confound study outcomes. In particular, occurrence of acute crises can profoundly alter inflammation, coagulation biology and affect P-selectin measurement. Therefore, of particular interest is the subgroup of steady state SCD patients that complete the 28-day study treatment period without experiencing an acute crisis. A subgroup analysis of the primary and key secondary endpoints will be conducted on this subset using the same analytic techniques.

#### 9.3.1 *Evaluable for toxicity*

All patients randomized will be evaluable for toxicity from the time of their first treatment with study supplement or placebo until 28 days after completion of the end of study visit.

#### 9.3.2 *Evaluable for objective response*

N/A

### 9.4 STATISTICAL ANALYSES

#### 9.4.1 *General Approach*

Please refer to sections 9.4.2, 9.4.3 and 9.4.6 for the general approach to statistical analysis.

#### 9.4.2 *Analysis of the Primary Endpoints*

The primary outcome will be the change in the soluble P-selectin level comparing baseline levels versus their respective response to IQ or placebo among randomized SCD patients. The proposed statistical method is an analysis of covariance model with follow-up P-selectin measurement (i.e. post-treatment measurement) as the dependent variable with baseline measurement and treatment assignment as the covariates. Significance in this pilot phase II study will be evaluated using a two-sided test with alpha level of 0.05.

*Abbreviated Title: IQ in sickle cell disease*

*Version Date: May 5, 2023*

#### 9.4.3 Analysis of the Secondary Endpoint(s)

The following endpoints are exploratory in nature:

- Compare baseline and end of study plasma protein disulfide isomerase activity
- Quantify baseline and end of study plasma tissue factor positive extracellular vesicle number
- Compare baseline and end of study tissue factor procoagulant activity
- Compare baseline and end of study platelet thrombin generation
- Compare baseline and end of study inflammatory cytokines
- Compare baseline and end of study plasma D-Dimer, TAT and PF1.2
- Compare baseline and end of study contemporary biomarkers of vascular endothelial function, specifically reactive hyperemia index.
- Assess safety and tolerability of IQ
- Assess adherence to oral IQ

Baseline and end of study measures of secondary end points will be similarly conducted using ANCOVA or Wilcoxon's rank sum test, if assumptions of normality are not warranted. We will explore statistical correlation between PDI activity, tissue factor EVs, tissue factor procoagulant activity and soluble P-selectin levels using Spearman's or Pearson's correlation coefficients.

Changes in hemoglobin, leukocytes, reticulocytes, platelets, LDH, Total and direct bilirubin, C-reactive protein, inflammatory cytokine panel and coagulation parameters from baseline after exposure to 28 days of Isoquercetin will be summarized.

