Since SCD patients have increased blood borne tissue factor, sustained thrombin generation and demonstrate features of platelet activation, plasma PDI inhibition, by restoring post-translational regulatory control of TF, might attenuate the associated hypercoagulable state. Such an approach is rationalized by observations of elevated plasma PDI activity SCD mice that when exposed to a pharmacologic PDI inhibitor demonstrated reduced vaso-occlusive crisis and microvascular thrombosis [13](#). In a phase II trial of patients with active cancer, the flavonoid Isoquercetin (IQ) (Quercet AG, Switzerland) robustly inhibited plasma PDI activity and favorably reduced soluble P-selectin, a biomarker predictive of VTE development [14](#). Besides, none of these patients experienced any increased risk of bleeding typically observed with exposure to warfarin or non-vitamin K oral anticoagulants [2-3](#). The salutatory benefits of lowering soluble P-selectin

*Abbreviated Title: IQ in sickle cell disease*

*Version Date: May 5, 2023*

in SCD patients are both reduced inflammation and TF expression. Therefore, our overall hypothesis is that therapeutic intervention with IQ would lower soluble P-selectin and simultaneously decrease the prothrombotic effects of TF without a concomitantly increased risk for bleeding. Evaluating the effects of IQ-mediated PDI inhibition on blood borne TF procoagulant activity and plasma soluble P-selectin will provide important insight into the pathophysiologic basis of the hypercoagulable state in SCD.

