## 4.2 SCIENTIFIC RATIONALE FOR STUDY DESIGN

This is a pilot phase II study and the number of subjects was chosen to provide good statistical power to detect a 25-30% reduction in plasma soluble P-selectin, a clinically meaningful thrombo-prophylactic benefit, similar to that observed in cancer patients (see power analysis in section 9). Such an effect would simultaneously offer the potential to explore the effects of PDI inhibition on post-translational regulatory control of TF. A parallel group double blind placebo-controlled study would be the most effective study design in which to enroll and complete the subject group in the proposed protocol with minimal risk for study withdrawal due to frequent acute painful crises.

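### The planned correlations among PDI activity, tissue factor measures and P-selectin do not say which visit, which scale or how treatment arm is handled; pooling post-treatment data across arms can produce correlation from the treatment effect alone

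*Protocol*

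**What the plan says.** The correlations rest on one sentence in protocol section 9.4.3: "We will explore statistical correlation between PDI activity, tissue factor EVs, tissue factor procoagulant activity and soluble P-selectin levels" "using Spearman's or Pearson's correlation coefficients". That is four markers, hence six pairs. The sentence names no visit, does not choose between levels and changes, and does not say whether the arms are pooled, separated or adjusted for. No significance level is attached. The section opens with "The following endpoints are exploratory in nature".

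Elsewhere arm is handled explicitly. Section 9.4.2 puts treatment assignment in the primary ANCOVA and sets a "two-sided test with alpha level of 0.05" for that test. Section 9.4.3 applies ANCOVA or a rank-sum test to the other endpoints. No comparable term is attached to the correlations. The SAP's list of secondary analyses and its account of how they will be done do not mention them.

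The rationale gives these relationships some weight. Section 2.1 says: "Evaluating the effects of IQ-mediated PDI inhibition on blood borne TF procoagulant activity and plasma soluble P-selectin will provide important insight" into the basis of the hypercoagulable state. Section 4.2 says the expected effect would allow the team to "explore the effects of PDI inhibition on post-translational regulatory control of TF".

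**The concern.** In a randomised trial with post-treatment data from both arms, arm is a common cause of every marker the drug changes. If isoquercetin lowers both PDI activity and P-selectin, treated patients cluster at low values of both and placebo patients at higher values of both. A plain coefficient over all patients picks up that separation even if, within each arm, a patient's PDI activity says nothing about that patient's P-selectin. The coefficient then partly restates two treatment effects that the between-arm comparisons already report.

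This sentence is the only planned analysis that relates the markers to one another; the rest take them one at a time. A pooled coefficient could be read as evidence that PDI inhibition drives the fall in P-selectin or tissue factor activity when it shows only that both moved under treatment. Because visit, scale and arm handling are open, the choice could also be made after unblinding.

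**Working it through.** **Inputs**
- P-selectin effect, section 9.2: 7.25 ng/ml, which is 25% of 29 ng/ml.
- Spread, section 9.2: "standard deviation of 8.4 with intra-person correlation of 0.60 for the two measurements".
- Allocation 1:1, section 4.1.
- Patients, SAP primary analysis: 46 randomised, 45 in the analysis set, one of these without follow-up, so 44 observed pairs. A 22/22 split is assumed.
- PDI effect, section 4.3: a 73.3% median change in PDI inhibitory activity in the cancer trial. No SD is given, so the shift in SD units is unknown; 0.5 to 3 SD is tried.
- Test level for the correlations: none stated; two-sided 0.05 is assumed.

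**The plan's own figure.** No figure is given for the correlations. The nearest is the ANCOVA sample size. The residual SD is 8.4 × √(1 − 0.60²) = 6.72. With the noncentral t distribution, power for 7.25 ng/ml at 15, 17 and 20 per arm is 81.3%, 86.1% and 91.3%, against the stated 80%, 85% and 90%. The inputs are therefore read as the plan meant them.

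**Standardised P-selectin shift**
- End-of-study level: 7.25/8.4 = 0.863 SD.
- Change from baseline: 7.25/(8.4 × √(2 × (1 − 0.60))) = 7.25/7.51 = 0.965 SD.

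**Correlation induced by pooling.** Take two markers independent within arm, with equal SDs in both arms, shifted by d1 and d2 SD in one arm of a 1:1 trial. Over all patients

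r = 0.25·d1·d2 / √[(1 + 0.25·d1²)(1 + 0.25·d2²)].

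- Both at 0.863: 0.186/1.186 = 0.16.
- PDI at 2, P-selectin at 0.863: 0.432/√(2 × 1.186) = 0.28.
- Only one marker shifted: 0.

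The critical |r| at n = 44 is 2.018/√(42 + 2.018²) = 0.297.

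**Chance of nominal p<0.05.** Simulated with normal markers, no within-arm correlation, 22/22, end-of-study levels, P-selectin shifted by 0.863 SD, at least 20,000 trials per row. Ranges cover Pearson, Spearman and repeat runs.

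| PDI shift (SD) | Expected pooled r | Pooled, p<0.05 | Adjusted for arm |
|---|---|---|---|
| 0 | 0.00 | 5% | 5% |
| 0.5 | 0.10 | 9–10% | 5% |
| 0.863 | 0.16 | 18% | 5% |
| 1.5 | 0.24 | 35–37% | 5% |
| 2 | 0.28 | 48–49% | 5% |
| 3 | 0.33 | 61–63% | 5% |

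**Variations**
- Changes instead of levels, both markers at the design effect (0.965 SD): expected r = 0.233/1.233 = 0.19, with p<0.05 in 23–24%. Changes alone do not help.
- Baseline levels only: r = 0, 5%.
- 20 per arm, both markers at 0.863 SD: 17%.
- All six pairs, four mutually unrelated markers each shifted by 0.863 SD: at least one nominally significant pair in 65% of trials, against 27% with no shift.

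**Precision after the fix.** Within one arm of 22 the critical |r| is 2.086/√(20 + 2.086²) = 0.42. If the true within-arm correlation were 0.3, power would be roughly one in four within a single arm and about one in two for the arm-adjusted estimate from both arms.

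**The case against.** The strongest reply is that the fault depends on a choice the protocol has not made. A reader might infer that the plan pools the arms, ignores treatment and uses levels in preference to changes. The documents do not say so: the word for levels may simply be the noun that goes with P-selectin, and the sentence is silent on visit and arm. Correlations at baseline, or within each arm, would be free of the problem. This stands, and the point is therefore that the analysis is unspecified. It does not dispose of the matter: a baseline-only analysis cannot speak to PDI inhibition, and the simplest pooled use of the named coefficients is the affected one.

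A reader might also infer that isoquercetin would by itself produce a significant correlation. At the only standardised effect the documents support, 0.86 SD, the expected coefficient is 0.16 against a critical 0.297, and 18% of trials cross the line. The larger percentages need PDI shifts the documents neither give nor exclude. So pooling can produce such a result; it need not.

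It is further fair that the section is exploratory, sets no test level and claims no mechanism, that the correlations enter no decision rule, and that the aims in 2.1 and 4.2 are also served by the randomised comparisons of each marker. This lowers the severity. An exploratory label does not, however, change what a pooled coefficient measures.

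Finally, conditioning on arm discards treatment-driven co-variation and so asks a narrower question, and neither version identifies mechanism. That is true and belongs in the report.

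**Conclusion.** The point holds as a gap in specification with a measurable consequence. If post-treatment levels or changes are pooled across arms, markers unrelated within arm can appear correlated: per pair, p<0.05 in about 9% to 49% of trials for PDI shifts of 0.5 to 2 SD with P-selectin at its planned effect, instead of 5%. Conditioning on arm restores about 5% in every scenario tried. These figures rest on normal markers, equal SDs in both arms, zero within-arm correlation, a 22/22 split, a two-sided 0.05 level that the plan does not set for these analyses, and an assumed PDI shift.

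Severity is minor to moderate. The primary analysis and the between-arm comparisons of the secondary markers are untouched. What is at risk is the interpretation of the one planned analysis that links PDI to tissue factor and P-selectin.

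**What to change.** In section 9.4.3 and the SAP, replace the open sentence with a specification along these lines: *Post-treatment associations among PDI activity, tissue factor-positive vesicles, tissue factor procoagulant activity and soluble P-selectin will be estimated as partial correlations of baseline-to-end-of-study changes, adjusted for treatment arm. Within-arm estimates will be shown descriptively. Baseline correlations will be reported separately. All are exploratory and do not by themselves establish mechanism.* Say in advance whether the rank or the linear version is used, and report estimates with confidence intervals for all six pairs.

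The cost is a few lines of text and code, and one degree of freedom, with no new data. The within-arm estimates, on about 22 patients each, will be imprecise. Co-variation caused by treatment is left to the randomised between-arm comparisons. Partial correlation of changes is one reasonable choice; the essential element is that arm is conditioned on and that the choice is fixed before unblinding.

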#### 9.4.4 Safety Analyses

The planned analyses will also include descriptive statistics on the incidence and severity of adverse events. The proportions of treatment related serious adverse events (TRSAEs) will be summarized using sample proportions and confidence intervals for binomial distributions. Safety will be summarized using descriptive statistics. Summaries will be produced for all treatment-emergent adverse events (TEAEs), related TEAEs (those considered by the Investigator as related to study treatment), SAEs, TEAEs leading to treatment discontinuation, and TEAEs Grade  $\geq 3$  in severity. Individual subject listings will be provided for any deaths, SAEs, TEAEs leading to interruption and TEAEs leading to treatment discontinuation.

#### Stopping rule

When the Bayesian posterior probability reaches 75% or higher, it will trigger a meeting of the DMSC. The prior distribution for the probability of a qualifying adverse event is given by a beta distribution with parameters  $a = 1.25$  and  $b = 3.25$ . For stopping rule purposes, qualifying AEs/SAEs will only be counted in the Isoquercetin arm. Monitoring for crossing the boundary and reporting to the DSMB, if necessary, will be done by the unblinded statistician.

The Table below summarizes the threshold numbers for the resulting boundary in the Isoquercetin arm, which would lead to a meeting of the safety committee to evaluate stopping or

*Abbreviated Title: IQ in sickle cell disease*

*Version Date: May 5, 2023*

modifying the study due to an excess number of qualifying AEs/SAEs. AEs will be counted for anyone randomized into the Isoquercetin arm regardless of whether they are withdrawn or lost to follow-up.

Table 5: Threshold numbers for resulting boundary

Number of subjects in the study	Hold enrollment if the number of subjects who have developed a qualifying AE/SAE is
$\leq 3$	2
$\leq 7$	3
$\leq 10$	4
$\leq 14$	5
$\leq 17$	6
$\leq 21$	7
$\leq 23$	8

We investigated the performance of the above stopping rule through simulation. In each simulation we generated a set of 23 independent Bernoulli trials; each representing an Isoquercetin-receiving patient with probability  $p$  for having a qualifying AE/SAE. For each simulation we determined if the stopping boundary would have been reached with consideration for halting or suspending the study. We conducted this simulation 100,000 times for each different true value of probability  $p$  and recorded the average number of Isoquercetin-receiving patients treated (it may be less than 23 if the study was stopped early) and the average number of qualifying AEs/SAEs observed. In addition, we show the proportion of the 100,000 simulations in which the stopping boundary was met. The table below summarizes the performance of the stopping rule under a number of different values for the qualifying AE/SAE probability  $p$ .

Table 6: Performance of the Stopping Rule under multiple scenarios for the qualifying AE/SAE Probability  $p$

Probability of a qualifying AE/SAE	0.15	0.20	0.25	0.30	0.40
Proportion of Stopped Studies	14%	28%	45%	63%	89%
Average number of subjects	20.7	18.7	16.2	13.5	8.9
Average number of qualifying AEs/SAEs	3.1	3.7	4.0	4.1	3.5

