## **7 STUDY INTERVENTION DISCONTINUATION AND PARTICIPANT DISCONTINUATION/WITHDRAWAL**

### **7.1 DISCONTINUATION OF STUDY INTERVENTION**

The supplement has a good safety record and we do not expect any significant adverse events. A DSMB will evaluate safety trial data based on the below triggers and if warranted, may recommend modification or even termination of this protocol. Stopping rules follow a Bayesian design. The stopping rule is designed to halt enrollment for further evaluation of study data by the safety committee and determination whether enrollment can continue, or the study should be modified or terminated. A Bayesian posterior probability will be calculated to determine the likelihood the probability of having a qualifying adverse event is 25% or more.

Qualifying AEs/SAEs for the stopping rule will be counted only in the Isoquercetin arm (and not in the placebo arm), will be monitored for reaching the stopping boundary by the unblinded statistician, and are any of the following three types of events:

- Any Grade  $\geq 3$  treatment related SAE (these include acute painful crises that are probably related to the intervention),
- Grade 4 bleeding, related to Isoquercetin ,
- Any non-hematological AE Grade  $\geq 3$  related to IQ

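### The hold boundary in Table 5 does not follow from the stated Beta(1.25, 3.25) prior and 75% trigger, and Table 6 describes the Table 5 boundary, not the stated rule

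*Protocol*

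**What the plan says.** Protocol section 7.1 defines the monitored quantity: "A Bayesian posterior probability will be calculated to determine the likelihood the probability of having a qualifying adverse event is 25% or more". The stopping-rule text in section 9.4.4 supplies the rest. The prior is a beta distribution with a = 1.25 and b = 3.25. The trigger is "When the Bayesian posterior probability reaches 75% or higher, it will trigger a meeting of the DMSC". On the arm counted it says "For stopping rule purposes, qualifying AEs/SAEs will only be counted in the Isoquercetin arm", and the unblinded statistician does the monitoring.

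Table 5 is then introduced as the consequence of these inputs: "The Table below summarizes the threshold numbers for the resulting boundary in the Isoquercetin arm". Its action column is headed "Hold enrollment if the number of subjects who have developed a qualifying AE/SAE is", and it reads: 2 for up to 3 subjects, 3 for up to 7, 4 for up to 10, 5 for up to 14, 6 for up to 17, 7 for up to 21, and 8 for up to 23.

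Table 6 gives simulated performance. The text says "In each simulation we generated a set of 23 independent Bernoulli trials", with 100,000 repetitions for each true rate. The row "Proportion of Stopped Studies" shows 14%, 28%, 45%, 63% and 89% at true rates of 0.15, 0.20, 0.25, 0.30 and 0.40.

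The SAP does not mention the safety stopping rule.

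**The concern.** A beta prior, a rate threshold and a posterior cut-off fix the boundary completely, so Table 5 can be checked exactly. If text and table disagree, a statistician who calculates the posterior and one who reads the table will act differently on the same data: one holds enrolment and the other continues.

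This is the trial's formal quantitative safety boundary. The DSMB would also have judged the rule on operating characteristics that belong to only one of the two versions.

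**Working it through.** **Inputs.** Rate threshold 0.25 (section 7.1). Prior Beta(1.25, 3.25), trigger 0.75, isoquercetin arm only, at most 23 patients (section 9.4.4). Table 5's subject count is read as isoquercetin patients, as its introduction indicates.

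**Step 1: reproduce Table 6 from Table 5.** An exact forward recursion over 23 independent patients, with the boundary checked after each one, gives:

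| True rate | Stop, exact | Stop, printed | Mean n, exact | Mean n, printed |
|---|---|---|---|---|
| 0.15 | 13.8% | 14% | 20.73 | 20.7 |
| 0.20 | 27.6% | 28% | 18.70 | 18.7 |
| 0.25 | 45.1% | 45% | 16.21 | 16.2 |
| 0.30 | 62.9% | 63% | 13.55 | 13.5 |
| 0.40 | 88.6% | 89% | 8.88 | 8.9 |

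Mean event counts agree too (3.11, 3.74, 4.05, 4.07 and 3.55, against the printed 3.1, 3.7, 4.0, 4.1 and 3.5). So Table 5 has been read correctly, and checking after every patient is what the simulation did.

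**Step 2: derive the boundary from the stated rule.** After s events in n patients the posterior is Beta(1.25 + s, 3.25 + n − s). The hold number is the smallest s for which P(p ≥ 0.25) is at least 0.75. For n = 1 to 23 this gives 1 (n = 1), 2 (n = 2–4), 3 (5–7), 4 (8–11), 5 (12–14), 6 (15–18), 7 (19–21) and 8 (22–23).

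It agrees with Table 5 at 19 of the 23 sizes. The four exceptions are:

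| n | s | Posterior | P(p ≥ 0.25) | Table 5 needs |
|---|---|---|---|---|
| 1 | 1 | Beta(2.25, 3.25) | 0.766 | 2 (cannot be reached) |
| 4 | 2 | Beta(3.25, 5.25) | 0.779 | 3 |
| 11 | 4 | Beta(5.25, 10.25) | 0.761 | 5 |
| 18 | 6 | Beta(7.25, 15.25) | 0.760 | 7 |

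The table is the later to hold in every case. The posteriors exceed 0.75 by 1 to 3 percentage points, so rounding does not explain the gap. No posterior equals 0.75, so reading the trigger as strictly greater changes nothing.

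**Step 3: operating characteristics of the stated rule.** The same recursion gives:

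| True rate | Table 6 | Stated rule | Difference (points) | Stated rule, no hold at n = 1 | Difference (points) |
|---|---|---|---|---|---|
| 0.15 | 14% | 25.2% | 11.2 | 17.2% | 3.2 |
| 0.20 | 28% | 39.6% | 11.6 | 32.0% | 4.0 |
| 0.25 | 45% | 55.6% | 10.6 | 49.5% | 4.5 |
| 0.30 | 63% | 70.8% | 7.8 | 66.6% | 3.6 |
| 0.40 | 89% | 91.4% | 2.4 | 90.1% | 1.1 |

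At a true rate of 0.25 the mean number of isoquercetin patients is 13.1 under the stated rule, 15.2 if no hold is allowed at n = 1, and 16.2 in Table 6. The simulation error of a proportion near 45% with 100,000 runs is √(0.45 × 0.55 / 100,000) ≈ 0.16 points, so chance does not account for the differences.

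**Step 4: what would generate Table 5.** With the 75% trigger, Beta(1.25, 3.75) reproduces Table 5 at every n where a hold is possible, and so does Beta(1.5, 4.5). With the stated prior, Table 5 results if the cut-off lies above 0.7792 (2 in 4 must not trigger) and no higher than 0.7807 (7 in 21 must trigger), for example 78%.

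**The case against.** The two tables agree with each other, and the hold instruction is printed in Table 5. On that reading the DSMB was given correct performance figures for the boundary actually used, and only the sentence stating the prior is off. A single digit would explain it: b = 3.75 gives a prior mean of 1.25/5.00 = 0.25, equal to the monitored threshold, whereas the printed prior has mean 1.25/4.50 = 0.278. This is plausible, but it concedes that a printed figure is wrong. Nor is it the only explanation, as step 4 shows. The protocol does not say that the table takes precedence over the calculated posterior.

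Most of the headline gap comes from n = 1. That is right, and it is why the figures are also shown without it. Differences of 3.2 to 4.5 points remain at rates of 0.15 to 0.30, and the conflicts at 4, 11 and 18 patients are untouched.

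Other safeguards limit the harm. Section 8.4.3 suspends enrolment after any treatment-related SAE, the DSMB can ask for safety data at any time, and crossing the boundary prompts a review and not automatic termination. This stands, although section 7.1 also counts related non-haematological grade 3 or higher events that need not be serious.

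Finally, the SAP of 7/20/22 reports 46 participants randomised, which is the accrual ceiling, so a hold on enrolment had little left to govern. That makes the correction largely retrospective. The protocol dated May 5, 2023 still carries the contradiction.

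**Conclusion.** The concern holds. The written prior and trigger do not produce Table 5: they call for a hold one event earlier at 1, 4, 11 and 18 isoquercetin patients. Table 6 describes the Table 5 boundary. At a true rate of 0.15 the written rule triggers in 25% of trials against the printed 14%, or in 17% if the first-patient trigger is left out. The gap narrows to 1 to 2 points at a rate of 0.40.

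The result rests on the figures printed in sections 7.1 and 9.4.4, on Table 5 counting isoquercetin patients, and on a check after each patient. The match with Table 6 supports the last two. The primary efficacy analysis is not affected. The calculation shows that at least one printed figure is wrong. It does not show which, and it does not say which boundary the trial should have used.

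**What to change.** Reconcile section 7.1, the prior and trigger in section 9.4.4, and Tables 5 and 6. There are two ways to do this:

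- state the prior and cut-off that actually generated Table 5, leaving both tables as they are; or
- keep Beta(1.25, 3.25) with 75% and recompute Tables 5 and 6, saying explicitly whether the rule applies from the first patient.

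Whichever is chosen, say whether the table or the calculated posterior governs, and have the DSMB confirm in writing which was operative. Because 46 participants had been randomised by the SAP date, the unblinded statistician should also check whether the isoquercetin counts at 1, 4, 11 or 18 patients ever met the written rule without meeting the table, and record the answer.

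The cost is a wording correction or two recomputed tables, a short look-back and a DSMB confirmation. No additional patients or procedures are needed.
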